3.1.4 Study Completer Population

The PCP study completer population consists of the randomized PCPs who do not indicate early withdrawal on the Provider Eligibility Review (PCP) form.

3.2 Patient Participant Analysis Populations

3.2.1 Prescreened Population

The prescreened population consists of all patient participants who took the anonymous prescreening survey (Healthy Living Study (HLS) Survey).

3.2.2 Screened Population

The screened population consists of all patient participants who provided verbal consent at the initiation of the screening process.

3.2.3 Intent-to-Treat Population

The Intent-to-Treat (ITT) population consists of all enrolled patient participants whose PCP / PCP cluster is randomized to STOP or EUC. The ITT population will be analyzed according to the randomization assignment of their PCP regardless of potential exposure to the opposite assignment. The ITT population is used for the primary outcome analysis.

3.2.4 Complete Case Population

The complete case population is a subgroup of the ITT population which includes the patient participants who have no missing data for the variables of interest for the primary outcome analysis. The variables of interest include the primary outcome data collected in Months 1-6 and the baseline value of risky opioid use.

3.2.5 Per Protocol Population

The Per Protocol (PP) population is a subgroup of the ITT population with the following patient participants excluded:

- Had visits with PCPs in the opposite treatment arm as collected on the Chart Abstraction Visits (EMV) form. If the patient participant does not have the EMV form (e.g. the site did not do chart abstraction because the patient participant withdrew consent), they will be excluded from the PP population.

- Deviated from the protocol in terms of intervention exposure, including the participants who were shown the video doctor for the opposite treatment arm.

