10.3 Randomization

After providing written/electronic informed consent, PCPs will be randomly assigned in a 1:1 ratio to (1) STOP Intervention, or (2) Enhanced Usual Care (EUC). In study sites where PCPs practice in teams, randomization will be at the team level (for example, if PCPs practice in teams of two, the two PCPs will be treated as one cluster in the randomization). Randomization will be stratified by site and will occur at each site prior to the intervention start date. The randomization procedure will be conducted through a process set up by the CTN Data and Statistics Center (DSC), and the randomization sequence will be unknown to staff. The DSC statistician will review the randomization data on a regular basis to ensure that the scheme is being implemented according to plan.

Patient participants receive the intervention to which their PCP is assigned. While randomizing at the PCP level introduces the possibility of contamination that has the potential to reduce the observed intervention effect size, this strategy is similar to our study team's previous studies (TOPCARE randomized PCPs, QUIT randomized patients) that had significant findings. Contamination could arise if patient participants change PCPs or make appointments with PCPs in the opposite treatment arm, or if PCPs drop out of the study (which would force a change in PCP upon their patients). These instances of contamination will be recorded, and the contamination data may be summarized with the study findings.

After the baseline PCP encounter, differences in clinical care received by the patient participant are driven primarily by the NCM, who interacts directly with the patient participant and provides advice to the PCP about the patient participant's management. To guard against contamination, NCMs will be instructed to communicate only with PCP and patient participants who are in the intervention condition. To facilitate this, NCMs will have a list of patients who are enrolled in the study and have a PCP assigned to the intervention condition. In the relatively unlikely event that a patient participant in the EUC group has a visit with STOP intervention PCP after the baseline visit (for example, if the intervention PCP is covering for the patient's regular provider), the NCM will not interact with the patient participant.

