11.5.12 Chart Review

A structured chart review will be conducted by research staff to assess the following secondary outcome measures. Each measure is extracted for the period 12 months prior to the baseline visit, and 12 months after the baseline visit. Patient participants give consent for gathering this information when they enroll in the study.

- Prescription of opioid medications, including medication name, dose, frequency, and number of pills to be dispensed. This will be converted into MME by day (assuming maximum medication used) over the 12-month period.
- High-dose opioids (defined as >90 MME daily).
- Prescriptions for benzodiazepines, converted into standard medication (e.g., diazepam) equivalent dose, and converted into daily doses. It will also allow calculation of overlap of opioids and benzodiazepines.
- Prescription of naloxone kits: date of prescription.
- Monitoring of patient participants with opioid use: toxicology testing, diagnosis of OUD.
- Primary care visits and missed appointments at the study clinic.
- Number of visits to a study PCP randomized to the opposite treatment arm

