- a. H2.14. Health-related quality of life is measured at baseline and at 6 and 12 months (SF-12)
- b. H2.15. ED and hospital utilization is measured using participant self-report of acute care events (ED visits, hospitalizations for medical reasons, hospitalizations for detoxification), collected at baseline and at 6 and 12 months.

Measures of provider-level outcomes.

Measures of provider treatment practices are collected from the EHR at baseline and 12 months, for patient participants. The data extracted will be for the period beginning 12 months prior to start of the intervention, through 12 months after the last patient participant is enrolled.

- 1. H3.1. Prescriptions for opioids: number of patient participants receiving prescriptions for high-dose opioids (>90 MME); moderate-dose opioids (50-90 MME); and any opioids: number of prescriptions; daily prescribed dose; and total number of days prescribed.
- 2. H3.2. Prescriptions for benzodiazepines: number of patient participants receiving benzodiazepine prescriptions and number receiving both chronic opioid and benzodiazepine prescriptions: number of prescriptions; daily prescribed dose, and total number of days prescribed
- 3. H3.3. Prescriptions for naloxone: number of patient participants receiving at least 1 prescription
- 4. H3.4. Urine Drug Screens: number ordered and completed for each patient participant
- 5. H3.4. Diagnosis of OUD: number of patient participants receiving a new diagnosis of OUD during the study period
- 6. H3.4. Primary care visits: number of scheduled visits per patient participant

Other outcome measures.

The following additional measures will be collected to assess exploratory outcomes, characterize domains from our conceptual model, and may be used to adjust models of the primary and secondary outcomes. These measures are collected at the baseline study visit and at the study visits specified in Tables 5 and 6 (schedule of assessments).

- 1. Demographic characteristics and insurance status.
- 2. Patient participants' self-assessments of readiness to change risky opioid use and other substance use will be measured using two items that query self-reported readiness and confidence to change, rated on a 10-point scale.

3. Social support will be assessed using the PROMIS instrumental and emotional health short forms.
4. Patient engagement in primary care (Exploratory Objective 1): Number and frequency of kept appointments and missed appointments for primary care visits.

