7.0 EFFICACY ANALYSIS

7.1 Definition of the Primary Outcome Measure

The primary outcome (H1.1) measure is self-reported number of days of risky (illicit or nonmedical) opioid use in the past 180 days, assessed at 6 months after the baseline visit using single items based on questions used in the Addiction Severity Index (ASI) [3,4], and Current Opioid Misuse Measure (COMM) [5,6]. Participants are asked to specify the number of days of illicit opioid use and of nonmedical opioid use in the past 30 days (range is 0-30 days). Illicit opioid use includes use of heroin or synthetic opioids. Nonmedical opioid use includes using prescribed opioids more than prescribed (e.g., taking 2 tablets when the prescription indicates a dose of 1 tablet) or taking pharmaceutical opioids that were not prescribed to the individual taking them. Prescription opioids may be prescribed by the participating PCP or by another medical provider. The measure is calculated as the sum of all days of use reported on the assessments of past 30-day drug use for the first 6 months (i.e., the sum of days of use from the measures collected on day 30, day 60, day 90, day 120, day 150, and day 180).

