4. To gain analytical power, a general rule of thumb is that 10-20 observations should be used for estimating a parameter [12]. If the number of covariates after steps 2 and 3 is more than 10, the distributions of the remaining covariates will be compared by intervention group to select the potential confounders associated with baseline imbalances.

Multiple imputation will not be performed in the individual-level covariate adjusted regression model. The estimates of treatment effect will be compared between the regression models with and without the individual-level covariate adjustment to assess the robustness of the conclusion drawn from the primary analysis.

Subgroup analyses for sex (Male, Female), age (18 – 54 years, 55 years or greater), race (Black, White, Other) and ethnicity (Hispanic or Latinx, Not Hispanic or Latinx) will be performed as required by the NIH [13]. Responses of “Unknown,” “Don’t know” and “Refused to answer” will not be analyzed. These subgroup analyses will utilize the same mixed-effect model as for the primary outcome analysis, but with the inclusion of an interaction term between treatment arm and the demographic subgroup. Contrasts will be used to test for statistically significant differences in the primary outcome hypothesis by subgroup.

An analysis using the Per Protocol (PP) population will be performed using the same methods as described in Section 7.2.2. This population will exclude participants who had appointments with PCPs in the opposite treatment arm or had deviation from the protocol in terms of intervention exposure including the participants who were shown the wrong video doctor. No multiple imputation will be conducted for the PP population.

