Measures of provider treatment practices are collected from the EHR at baseline and 12 months, for patient participants. The data extracted for each patient participant will be for the period beginning 12 months prior to study participation, through 12 months following enrollment.

1. H3.1. Prescriptions for opioids: number of patient participants receiving prescriptions for high-dose opioids (>90 MME); moderate-dose opioids (50-90 MME); and any opioids: number of prescriptions; daily prescribed dose; and total number of days prescribed.
2. H3.2. Prescriptions for benzodiazepines: number of patient participants receiving benzodiazepine prescriptions and number receiving both chronic opioid and benzodiazepine prescriptions: number of prescriptions; daily prescribed dose, and total number of days prescribed.

3. H3.3. Prescriptions for naloxone: number of patient participants receiving at least 1 prescription.
4. H3.4. Urine Drug Screens: number ordered and completed for each patient participant.
5. H3.4. Diagnosis of OUD: number of patient participants receiving a new diagnosis of OUD during the study period.
6. H3.4. Primary care visits: number of scheduled visits per patient participant.

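### The per-protocol exclusion for opposite-arm PCP visits has no time window, so visits outside the 180-day outcome period can remove participants

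*SAP*

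**What the plan says.** SAP 3.2.5 defines the PP population as the ITT population minus three groups: participants who "Had visits with PCPs in the opposite treatment arm as collected on the Chart Abstraction Visits (EMV) form"; participants with no EMV form; and participants whose intervention exposure departed from protocol, such as being shown the other arm's video. SAP 7.4 repeats the first ground: "This population will exclude participants who had appointments with PCPs in the opposite treatment arm". Protocol 14.6 has the same rule. None of the three places gives a start or end date.

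The source of the visit information is the chart review. Protocol 11.5.12 says "Each measure is extracted for the period 12 months prior to the baseline visit, and 12 months after the baseline visit", and the list that follows includes "Number of visits to a study PCP randomized to the opposite treatment arm".

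The outcome analysed in the PP population is the primary outcome, defined in SAP 7.1 as "the sum of days of use from the measures collected on day 30, day 60, day 90, day 120, day 150, and day 180". SAP 7.4, the list of planned outputs in SAP 17.0 and shell Table 40 show no PP analysis of any other outcome.

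**The concern.** The PP analysis is meant to show what the primary comparison looks like without participants exposed to the other arm. That requires an exclusion tied to exposure that could have influenced the outcome. A rule with no dates, applied to a form that may span two years, also catches visits that could not.

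Two kinds of visit are clearly wrong to count. A visit to a covering PCP in month 11 comes after the last survey that feeds the outcome, so removing that participant selects on a later event. A visit made before the PCP was randomized is not crossover, because that PCP had no arm.

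The PP analysis also uses no imputation (SAP 7.4; Table 40), so needless exclusions shrink a sample already limited to participants with complete data. A gap between the PP and ITT estimates could then be read as evidence about contamination when part of it comes from the exclusion rule.

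**Working it through.** The plan states no PP sample size, crossover rate or opposite-arm visit rate, so there is no figure to reproduce. The check compares the windows and then illustrates how far the answer depends on an unknown rate.

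**Windows**
- Chart review (Protocol 11.5.12): 12 + 12 = 24 months around baseline.
- SAP 7.7, for provider measures: the same span, "beginning 12 months prior to study participation, through 12 months following enrollment".
- Protocol 14.2.2, for provider measures: a calendar window, "beginning 12 months prior to start of the intervention, through 12 months after the last patient participant is enrolled".
- Primary outcome (SAP 7.1): Days 1-180, or 6 months.

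Share of the chart window inside the outcome period: 6/24 = 25% (in days, 180/730 = 24.7%). If the EMV form covers follow-up only: 6/12 = 50%.

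**What contamination means in the protocol.** Protocol 10.3 illustrates it with a visit after baseline, for example "if the intervention PCP is covering for the patient's regular provider". The PP rule is wider than that.

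**When an arm exists.** Protocol 6.2 has PCPs enrolling about 1-2 months before the intervention starts, and Protocol 8.2.1 lets further PCPs join during recruitment. For early enrollees, most of the 12-month look-back therefore predates randomization. Even a visit after baseline can precede the randomization of a PCP who joined late.

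**Illustration (assumed rates, not from the documents).** Let opposite-arm visits follow a Poisson process at a constant rate of L per participant per 24 months.
- Excluded under the undated rule: 1 - exp(-L).
- With at least one visit in Days 0-180: 1 - exp(-L/4).
- Share of visit-based exclusions with an in-window visit: (1 - exp(-L/4)) / (1 - exp(-L)).

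| L | Excluded of 300, 24 months | Of 300, Days 0-180 | In-window share |
|---|---|---|---|
| 0.1 | 28.5 | 7.4 | 26% |
| 0.5 | 118.0 | 35.3 | 30% |
| 1 | 189.6 | 66.4 | 35% |
| 2 | 259.4 | 118.0 | 46% |
| 3 | 285.1 | 158.3 | 56% |

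The in-window share passes 50% at L of about 2.4. If visits cluster in some participants (gamma-mixed counts, k = 0.25 to 1), it does so at L of about 1.2 to 2.0. If visits are rare but concentrated in Days 0-180, an intensity there of w times the rest gives 6w/(6w + 18) = 0.5, so w = 3 is enough.

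**Other grounds.** If a share m of all PP exclusions comes from a missing EMV form or wrong exposure, out-of-window visits account for at most about (1 - m) x 75%. With m = 1/3 that is 50%.

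**The case against.** A reader might infer that most PP exclusions will be irrelevant to the 6-month outcome. The documents do not support that. They give neither the rate nor the timing of opposite-arm visits, the majority reverses under the higher, clustered or front-loaded patterns shown above, and two of the three exclusion grounds do not depend on visit dates.

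It is also too strong to say that no visit before enrolment could matter. Protocol 10.6.2 allows the nurse care manager to offer care management to any patient of a STOP PCP, and recruitment runs for about 24 months, so a late enrollee's look-back can fall after PCP randomization. That route is narrow, because the same section bars such care for patients of EUC PCPs, but a patient who changed PCP could have had real exposure.

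Nor do the documents show that exclusions would be unbalanced between arms. H3.4 expects more frequent visits under STOP providers, which does not imply more visits to the opposite arm.

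The EMV form itself is not reproduced, so it may already separate visits before and after enrolment. Protocol 11.5.12 introduces its list as secondary outcome measures, which opposite-arm visits are not, so the 24-month span may not have been intended for that item. Finally, the PP analysis is supplemental, no decision rule depends on it, and Protocol 10.3 provides for contamination to be recorded separately.

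These points limit the size and importance of the problem. They do not supply the missing window: even on a follow-up-only reading, Months 7-12 would still trigger exclusion.

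**Conclusion.** The point holds as a defect in a stated rule. The PP exclusion has no time limit, its documented source covers 12 months on each side of baseline, and its only use is for an outcome complete at Day 180. Applied literally, it can remove participants for visits after Day 180 or before the PCP was randomized, neither of which is crossover relevant to that outcome.

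The number affected is unknown. What the documents fix is that 6 of 24 chart months fall in the outcome period, or 6 of 12 on a follow-up-only reading. The counts in the table rest on an assumed constant visit rate and are not predictions. Protocol 10.3 regards a visit by an EUC participant to a STOP PCP after baseline as fairly improbable, which suggests the lower rows, but this is a judgement and not a rate. The consequence is confined to one supplemental analysis; the ITT primary analysis does not change.

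**What to change.** In SAP 3.2.5 and 7.4, limit the criterion to visits with an opposite-arm study PCP that took place:
- after that PCP's randomization; and
- between the baseline visit and Day 180, counting a PCP appointment integrated with the baseline visit even if it came just before formal enrolment.

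The second condition needs this wording because SAP 3.3.2 sets Day 1 at enrolment, while Protocol 10.1.2 asks staff to delay enrolment until after an upcoming PCP appointment. A strict Day 1 start could miss the appointment at which brief advice may be given.

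Report PP exclusions by arm, reason and timing. SAP 3.5 and Table 40 already give PP numbers by arm, but not why or when participants were excluded, and the Table 40 count also reflects missing data. The timing breakdown would show any visits before baseline but after randomization, which the revised rule leaves in.

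SAP version 2.0 already adds a post hoc analysis. If results are known, keep the existing PP analysis and report the dated rule as a labelled sensitivity version.

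The cost is one sentence in each SAP section and a small table. If the EMV form holds counts without dates, charts with a non-zero count must be re-checked; how many that is depends on the unknown visit rate.

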3.2.6 Primary Outcome Available Population

The primary outcome available population is a subset of the ITT population and consists of the patient participants who have each of the first 6 months of the Healthy Living Monthly Survey (HLM) collected to calculate the primary outcome of days of risky opioid in the past 180 days. The algorithm of calculating the number of days of risky opioid use measured in HLM is described in Section 7.2.1.

3.2.7 Primary Outcome Not Available Population

The primary outcome not available population is a subset of the ITT population and consists of the patient participants who missed one or more of the variable(s) used to calculate the primary outcome in the first 6 months of the Healthy Living Monthly Survey (HLM) due to dropout or intermittent missingness. The primary outcome not available population is the complementary set to the primary outcome available population.

3.2.8 Study Completer Population

The patient participant study completer population consists of the patient participants who finish the 12-month follow-up visit as indicated in the Study Completion Form (STC).

3.2.9 Safety Population

The safety population includes all patient participants who are enrolled in the study. This population should be summarized according to the randomization assignment of their PCPs since the study is designed as a minimal risk study and the intervention components are not anticipated to cause related adverse events or serious adverse events.

3.3 General Definitions

3.3.1 Risky Opioid Use

Risky opioid use is defined as nonmedical use of prescribed opioids (taking a higher dose or taking an opioid more frequently than prescribed), any use of illicit opioids, or taking pharmaceutical opioids that were not prescribed to the individual taking them.

3.3.2 Study Day

Study Day 1 is defined as the day of patient participant enrollment.

3.3.3 Study Month

The Healthy Living Monthly (HLM) Survey is collected monthly for 12 months following patient participant enrollment. Study Months are defined as 30 days. Participants are asked to specify the number of days of substance use in the past 30 days (range is 0-30 days). Study Months 1-12 are defined as follows: day 30, day 60, day 90, day 120, day 150, day 180, day 210, day 240, day 270, day 300, day 330, and day 360.

3.3.4 Baseline Value

The baseline values for HLM, TAPS Tool, Current Opioid Misuse Measure (COMM), and Readiness to Change assessments are collected in the prescreening survey and all other baseline values are collected at the screening and baseline visits.

3.3.5 Safety Event

Safety reporting will be limited to reporting the following Safety Events: non-fatal alcohol or drug overdose events, suicidal ideation, hospitalizations, emergency department (ED) visits, and deaths.

Because this is a minimal risk study with no pharmacological intervention, causally related Adverse and Serious Adverse events are not anticipated for this study. Collection and reporting of Adverse Events and Serious Adverse Events is not required in the data system.

3.4 Scoring Conventions

For patient participant assessments that require scoring and that will be summarized in the baseline demographic summary (Section 5.2) and/or used as potential covariates (Section 7.4), the following scoring algorithms will be used:

Assessment (eCRF)	Name of Score	Number of Items	Score Range	Scoring Algorithm
Current Opioid Misuse Measure (HLS (baseline), CMM (other timepoints))	COMM Score	17	0-68	Sum of the seventeen 0-4 rated items
Psychiatric Diagnostic Screening Questionnaire (PDQ)	Alcohol Use Disorder Score	6	0-6	Sum of the yes (1)/no(0) alcohol items
Psychiatric Diagnostic Screening Questionnaire (PDQ)	Drug Use Disorder Score	6	0-6	Sum of the yes (1)/no(0) drug items
Overdose Risk Behavior (ORB)	Overdose Risk Behavior Score	9	0-34	Sum of the eight 0-4 rated items and one 0-2 rated item
Brief Pain Inventory Short Form (BPI)	Pain Severity Score	4	0-10	Average of the four 0-10 rated severity items
Brief Pain Inventory Short Form (BPI)	Pain Functioning or Interference Score	7	0-10	Average of the seven 0-10 rated interference items
PROMIS Anxiety Short Form (PMA)	Anxiety Score	8	0-32	Sum of the eight 0-4 rated items
Patient Health Questionnaire-8 (PHQ)	Depression Score	8	0-24	Sum of the eight 0-3 rated items
PROMIS Sleep Disturbance Short Form (PMS)	Sleep Disturbance Score	4	4-20	Sum of the four 1-5 rated items with last two items reversed scored
Short Form 12 (SFM)	Health related Quality of Life (QoL): Overall Score		0-100	Scored using QualityMetric proprietary software
Short Form 12 (SFM)	Health Related QoL: Mental Health Component Score		0-50	Scored using QualityMetric proprietary software
Short Form 12 (SFM)	Health Related QoL: Physical Health Component Score		0-50	Scored using QualityMetric proprietary software

When participants are missing one or more of the items that comprise the score, prorated scores by averaging the available items will be used to compute the score. The prorated score is calculated using the following equation:

$$T_P = \left(\frac{T_R}{N_R} \right) \times N_T$$

where

T_P = Prorated total score

T_R = Total raw score based on those items with a response

N_R = Number of items with a response

N_T = The total number of items which comprise the score.

A prorated score is computed when less than 20% of the items are missing. Otherwise, the score is set to missing.

The Overdose Risk Behavior Questionnaire consists of 9 items (eight 0-4 rated items and one 0-2 rated item). Using the above rule, the prorated score will be calculated when no more than 1 item is missing. If the missing item is one of the items on the 0-4 rating scale, the prorated score is derived by averaging the 7 remaining items on the 0-4 scale and multiplying by the number of items with a response and then adding the raw score of the item on the 0-2 scale using the following equation:

$$T_{ORB} = \left(\frac{T_{0-4}}{N_{R(0-4)}} \right) \times N_{T(0-4)} + T_{0-2}$$

where

T_{ORB} = Prorated total overdose risk behavior score

T_{0-4} = Total raw score based on those items on the 0-4 rating scale which have a response

$N_{R(0-4)}$ = Number of items on the 0-4 rating scale which have a response

$N_{T(0-4)}$ = Total number of items on the 0-4 rating scale; it should be 8

T_{0-2} = Raw score of the item on the 0-2 rating scale.

If the one missing item is the item on the 0-2 rating scale, the missing item score is imputed by averaging the 8 available items on the 0-4 rating scale and multiplying by $\frac{1}{2}$. The prorated score is then derived by adding the total score from the 8 items on the 0-4 scale and the imputed score of the item on the 0-2 rating scale using the following equation:

$$T_{ORB} = T_{0-4} + \left(\frac{T_{0-4}}{N_{T(0-4)}} \right) \times \frac{1}{2}$$

where

T_{ORB} = Prorated total overdose risk behavior score

T_{0-4} = Total raw score based on those items with 0-4 rating scale

$N_{T(0-4)}$ = Total number of items with 0-4 rating scale; it should be 8.

The scores for Short Form 12 (SFM) will use the missing data estimation method (Maximum Data Recovery) provided within the Quality Metric proprietary software.

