Self-reported overdose risk behavior will be measured by the overdose risk behavior questionnaire (which gives a numeric score) at baseline, 6, and 12 months. Mean scores will be compared between groups at 6 and 12 months in a random-effect regression model. Also, the total number of non-fatal opioid-related overdose events in the past 3 months will be measured at baseline, 6, and 12 months. Mean numbers of opioid-related overdose events will be compared between groups in a random-effect regression model (H 2.10).

Changes in pain-related symptoms and functioning from baseline as measured by the BPI (which calculates a numeric score) will be compared between treatment arms using Mann-Whitney tests. As the scientific goal is to demonstrate no worsening of pain, a noninferiority test will compare changes in BPI score between treatment and control groups with a minimal clinically important difference of 1 based on the IMMPACT recommendations. A secondary analysis will distinguish the effect of STOP on the change in pain-related symptoms for participants with opioid prescriptions at baseline, and the effect for those who were enrolled solely due to illicit use.

Symptoms of depression, suicidality, anxiety (H2.12), and poor sleep (H2.13) in the past two weeks will be measured at baseline and quarterly (PHQ-8) and at baseline, 6, and 12 months (PROMIS anxiety and sleep measures and PSS). Mean values will be compared between treatment arms in random-effect regression models.

Health-related quality of life (H2.14), and ED and hospital utilization (H2.15) in the past two weeks will be measured at baseline and at 6 and 12 months. Mean values will be compared between treatment arms in random-effect regression models.

Similar models will be fit for the Aim 3 objectives, but these will use provider rather than patient as the unit of observation, so will not need a PCP effect to adjust for within-PCP correlation. Regression models will be used to compare number of prescriptions of high-dose opioids within 12 months of follow-up between treatment arms as well as number of days prescribed during 12 months follow-up. Similar analyses will be done for number of prescriptions for any opioids or benzodiazepines, numbers of naloxone kits prescribed, numbers of urine toxicology tests ordered and completed, and number of patient participants receiving a new diagnosis of OUD.

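### The general proration equation in SAP 3.4 returns a total, so a BPI interference score with one of its seven items missing comes out at seven times its intended value, up to 70 on a 0-10 scale

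*SAP*

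**What the plan says.** The scoring table in SAP 3.4 (Scoring Conventions) gives the BPI Pain Functioning or Interference Score a range of 0-10 and the algorithm "Average of the seven 0-10 rated interference items". BPI severity is also an average: "Average of the four 0-10 rated severity items". The other scores that the general rule can reach (COMM, the two PDSQ scores, PROMIS Anxiety, PHQ-8 and PROMIS Sleep) are sums.

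Below the table comes the rule for missing items: "When participants are missing one or more of the items that comprise the score, prorated scores by averaging the available items will be used". The SAP then gives the equation for the prorated score, T_P = (T_R/N_R) x N_T, with these definitions:

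- "T_P = Prorated total score"
- T_R: "Total raw score based on those items with a response"
- N_R: the count of answered items
- N_T: "The total number of items which comprise the score"

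The threshold is: "A prorated score is computed when less than 20% of the items are missing. Otherwise, the score is set to missing".

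Only two instruments get their own treatment. The Overdose Risk Behavior score has separate equations, and the SF-12 uses the vendor software's method. The BPI has no exception. The section opens by limiting its scoring to assessments used in the baseline summary (Section 5.2) or as potential covariates (Section 7.4).

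**The concern.** The last factor in the equation, N_T, turns the mean of the answered items back into a sum. For a summed scale that is the purpose of proration. For a score that is itself a mean, it leaves the result too large by a factor equal to the number of items. The table and the equation in the same section therefore give different values for the same participant.

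The interference score is used in two places that SAP 3.4 names. It is reported in the baseline tables (Table 18, repeated in Tables 19-21) as a mean with range 0-10. It is also a continuous candidate in the covariate-adjusted model of SAP 7.4 (Table 3). There, a sevenfold value would be a high-leverage point and could disturb the correlation and imbalance checks that select covariates.

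A third use is possible but not stated. For H2.11, SAP 7.8 says a "noninferiority test will compare changes in BPI score between treatment and control groups with a minimal clinically important difference of 1". A score on the wrong scale would matter there if this scoring were reused.

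**Working it through.** **Inputs (all SAP 3.4).** Equation T_P = (T_R/N_R) x N_T; prorate when less than 20% of items are missing; item counts, item ranges and score ranges from the scoring table.

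**Step 1: does the equation reproduce the stated maximum for summed scales?** Take the most items that may be missing, with every answered item at its maximum:

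| Score | Items missing | T_P | Stated maximum |
|---|---|---|---|
| COMM (17 items, 0-4) | 3 (17.6%) | (56/14) x 17 = 68 | 68 |
| PDSQ alcohol, PDSQ drug (6 items each, 0-1) | 1 (16.7%) | (5/5) x 6 = 6 | 6 |
| PROMIS Anxiety (8 items, 0-4) | 1 (12.5%) | (28/7) x 8 = 32 | 32 |
| PHQ-8 (8 items, 0-3) | 1 (12.5%) | (21/7) x 8 = 24 | 24 |

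It does, for each of them.

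**Step 2: BPI interference (7 items, 0-10, average).**

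- One item missing: 1/7 = 14.3%, so the score is prorated. Maximum T_P = (60/6) x 7 = 70, against a stated maximum of 10.
- Six answers of 5: (30/6) x 7 = 35, against an intended 5.
- Six answers of 1: (6/6) x 7 = 7, against an intended 1.
- Any affected participant with a mean item rating above 10/7 = 1.43 falls outside 0-10. Below that, the error stays inside the range.
- Two items missing: 2/7 = 28.6%, so the score is set to missing.

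Reading T_R as the mean of the answered items does not help: (10/6) x 7 = 11.67, still out of range.

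**Step 3: is any other score affected?** BPI severity is an average, but 1/4 = 25%, so it is set to missing and never prorated. PROMIS Sleep has four items and is likewise never prorated. The Overdose Risk Behavior score and the SF-12 have their own rules. Interference is the only score affected, and only with exactly one item missing.

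**Step 4: illustration of size.** The documents give neither the share f of participants missing exactly one item nor the score's distribution. Assume a true mean of 4 and SD of 2.7, with item missingness unrelated to the score. The arm mean rises by f x (7 x 4 - 4) = 24f. The SD follows from the mixture:

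Var = (1 - f)(2.7² + 4²) + f x 49 x (2.7² + 4²) - (4 + 24f)², where 2.7² + 4² = 23.29.

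| f | Rise in arm mean | SD (true value 2.7) |
|---|---|---|
| 0.5% | 0.12 | 3.45 |
| 2% | 0.48 | 5.06 |
| 3% | 0.72 | 5.88 |

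With about 150 participants per arm (300/2), 3% is four or five people.

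These are shifts in one arm. Under the same assumptions, the shift in the between-arm difference is 24 x (f_STOP - f_EUC), which is zero when the two rates are equal.

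**Step 5: a change score, if the rule were reused at follow-up.** A participant truly at 5 on both occasions shows a change of 5 - 35 = -30 if one baseline item is missing, and 35 - 5 = +30 if one follow-up item is missing.

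**The case against.** **The intended result is clear.** T_P is labelled a total and the table says the BPI score is an average, so a programmer could prorate the total and then divide by seven, giving T_R/N_R. The lead sentence also speaks of averaging the available items. This shows what was probably meant, but it is not what is written: the SAP says the prorated score itself is calculated with the equation, and no later division appears. A programmer who divides by seven gets the right number by departing from the text.

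**The error would show.** The Table 18 shell states the 0-10 range and prints the minimum and maximum, so a value of 35 would be noticed. That mostly stands. Participants with a mean rating of 1.43 or below would still pass unseen.

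**The covariate effect is limited.** Interference is one of 19 candidates in SAP Table 3. It can be dropped for missing data, for collinearity or at the imbalance step, and the model is supplemental. This stands.

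**H2.11.** A reader might infer that the pain noninferiority result is biased by a large part of its 1-point margin. The documents do not support that. SAP 3.4 confines itself to the baseline summary and potential covariates, and H2.11 is neither. The Lead Node, not the Data and Statistics Center, runs H2.11. The SAP also plans Mann-Whitney tests on BPI change, which a few extreme values hardly move, and it does not give the method of the noninferiority test. The 0.12 to 0.72 is a rise in one arm; similar missingness in both arms largely cancels it and leaves mainly extra variance, which makes noninferiority harder to show. In the other direction, the SAP gives no alternative BPI scoring rule, and the COMM row of the same table refers to later timepoints. Reuse is therefore possible, but not stated.

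**Conclusion.** The written rule is wrong for one score. A BPI interference score with exactly one of seven items missing comes out at seven times its intended value, up to 70 on a 0-10 scale. This follows from the SAP text alone and needs no assumption.

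The direct reach is baseline Tables 18-21 and the supplemental covariate-adjusted model. A reader might infer that the primary result is at risk because the score appears in a model of the primary outcome. It is not: the primary model in SAP 7.2.2 contains only treatment, site, baseline days of risky opioid use and a PCP intercept. Nor is this a fault in proration generally, since the equation is right for the summed scales to which it applies.

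Any effect on H2.11 is conditional on reuse of this scoring. It would then be chiefly added variance, with bias in proportion to the difference in item missingness between arms. The illustrated rise rests on an assumed mean of 4 and an assumed 0.5% to 3% of an arm affected; the SD figures also assume a true SD of 2.7. The correction is worth making because the text conflict is certain and the repair trivial.

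**What to change.** In SAP 3.4, state that the proration equation applies to summed scores only. Add that the BPI interference score, when less than 20% of its items are missing, is the mean of the answered items, T_R/N_R, at baseline and wherever the score is used at follow-up. That would also settle the scoring for H2.11. BPI severity needs no change, because it is never prorated under the threshold.

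The cost is one sentence and a check that the derivation program divides by the number of answered items. No new data are needed, and no other score changes.
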